3.1 Study Rationale

JUVÉDERM VOLITE without lidocaine was CE-marked in 2015, and the product with lidocaine was CE-marked in 2016. An open-label European study (V12-001) of JUVÉDERM VOLITE without lidocaine provided evidence of the product's safety and effectiveness in improving facial skin smoothness, and it serves as a feasibility study. This protocol is designed as a pivotal study to collect safety and effectiveness data on JUVÉDERM VOLITE XC for improvement in facial skin smoothness in order to support FDA product approval.

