10.3.1 Effectiveness Analyses

The effectiveness analyses will be based on the ITT population. All statistical tests will be 2-sided hypothesis tests performed at the 5% level of significance for main effects. All confidence intervals will be 2-sided 95% confidence intervals, unless stated otherwise.

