10.3.1.3 Secondary Endpoint Analysis

The first secondary effectiveness variable is subject responses on the FACE-Q Satisfaction with Skin questionnaire. The responses to the 12 items will be summed and converted to a scale score that ranges from 0 to 100 (higher score indicates more satisfaction) using the algorithm developed by the FACE-Q scale developers. The secondary effectiveness analysis is mean change from baseline in FACE-Q scale score at Month 1.

The other secondary effectiveness variable is the EI's assessment of fine lines on the cheeks on the AFLS. The AFLS responder rate at Month 1 will be analyzed in the same manner as the ACSS responder rate. Only subjects with baseline AFLS score of 2 on both cheeks or 3 on both cheeks will be included in the analysis.

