The primary effectiveness variable is the cheek skin smoothness based on the ACSS evaluated by EIs. The primary effectiveness endpoint is the ACSS responders at Month 1 defined as a participant who achieves at least a 1-point improvement from baseline on both cheeks based on ACSS. Month 1 refers to 1 month after the preceding treatment (initial or touch-up) for participants in the JUVÉDERM VOLITE XC treatment group or 1 month after randomization for participants in the no-treatment control group.

The null hypothesis is that there is no difference between the JUVÉDERM VOLITE XC treatment group and the no-treatment control group in the ACSS responder rate at Month 1. The alternative hypothesis is that there is difference between the JUVÉDERM VOLITE XC treatment group and the no-treatment control group in the ACSS responder rate at Month 1. These hypotheses are stated as:

$$H_0: P_v - P_c = 0$$

$$H_a: P_v - P_c > 0 \text{ or } P_v - P_c < 0$$

where P_v and P_c denote the responder rates for the JUVÉDERM VOLITE XC group at Month 1 after the preceding treatment (initial or touch-up) and for the no-treatment control group at Month 1 after randomization, respectively. The treatment effects between JUVÉDERM VOLITE XC and the no-treatment control group will be compared using the statistical method described in [Section 5.3.2](#). If the 2-sided p-value is less than 0.05 and the responder rate is greater for JUVÉDERM VOLITE XC than for the no-treatment control group, then JUVÉDERM VOLITE XC will be considered superior to the no-treatment control group.

3. Sample Size Determination

A sample size of 112 participants in the treatment group and 56 participants in the control group will provide 99.9% power to detect a difference of at least 40% in the responder rates on the ACSS between the groups, based on a 2-sided Fisher's exact test at the 5% level. The treatment group is assumed to have at least an 80% responder rate at Month 1, and the control group is assumed to have at most a 40% responder rate. The assumptions of responder rates are estimated from Allergan Study V12-001. Accounting for participant attrition of 20% during the study, 210 participants will be randomized at a 2:1 ratio to treatment group and control group. Randomization will occur within each study site.

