- The start and end of treatment periods listed above for the mis-treated participants (ie., randomized to Treatment and did not receive Volite or randomized to Control and was treated with Volite prior to the primary timepoint) will be determined based on the treatment received.
- For CP, effectiveness analyses and baseline characteristics will be performed on the mITT population using the “as-randomized” assignment.

JUVÉDERM VOLITE™ XC

- For TP, effectiveness and safety summaries will be performed on the VT population by treatment group.
- For RP, effectiveness and safety summaries will be performed on the VRT population.
- The baseline for applicable effectiveness endpoints and safety parameters will be the last non-missing assessment on or before the latter of randomization date or first treatment date in the control period
- The change from baseline values will be computed as the post-baseline value minus the baseline value.
- Continuous variables will be summarized by number of participants with observed values (n), mean, standard deviation (SD), median, 1st and 3rd quartiles (Q1, Q3), minimum (min), and maximum (max). Categorical variables will be summarized by the number of participants with observed values or events (n), frequency count (N1), and percentage of participants with observed values or events.
- All statistical hypothesis tests will be performed at the 2-sided 5% significance level, unless stated otherwise.
- In general, statistical analyses will be performed using SAS version 9.4 or higher. Adverse events (AEs) and medical history will be coded using the Medical Dictionary for Regulatory Activities (MedDRA) version 22.1 or higher.
- WHO Drug Dictionary will be used to code medications.

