5.4. Secondary Effectiveness Endpoints Analysis

5.4.1. Secondary Effectiveness Endpoints

The secondary effectiveness endpoints are change from baseline in FACE-Q Satisfaction with Skin overall converted score at Month 1 during the CP and AFLS responder at Month 1 during the CP.

Each participant's responses to the 12 items on the FACE-Q Satisfaction with Skin questionnaire will be summed and converted to a scale score that ranges from 0 to 100 (higher score indicates more satisfaction) using the algorithm developed by the FACE-Q scale developers (see [Sections 6.5.1](#) and [6.5.2](#) for details of derivation). The mean change from baseline in FACE-Q overall converted score at Month 1 will be calculated. The change from baseline value will be computed as the value for the postbaseline visit minus the baseline value. The analysis will be conducted using observed data (eg, no imputation for missing baseline or Month 1 FACE-Q scale scores).

An AFLS responder is defined as participant who achieves at least 1-point improvement from baseline on the AFLS scale (see Table 5-3) on both cheeks.

Table 5-3 **Allergan Fine Lines Scale**

Score	Grade	Description
0	None	No fine lines
1	Minimal	1-2 superficial lines
2	Moderate	3-5 superficial lines
3	Severe	Greater than 5 superficial lines; no crosshatching
4	Diffuse	Diffuse superficial lines; crosshatching

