5.4.2. Main Analytical Approach

For the secondary effectiveness endpoint of change from baseline in FACE-Q Satisfaction with Skin overall converted score at Month 1, a 2-sided 2-sample t-test, if the normality assumption holds, otherwise, the Wilcoxon rank-sum test will be used to compare mean change from baseline values between treatment and control groups using the mITT population.

For the secondary effectiveness endpoint of AFLS responder status at Month 1, the 95% CI will be provided for the proportion of responders for each treatment group. For comparison of treatment group versus control group at Month 1, the responder rate difference, 95% CI for the risk difference and p-value will be estimated based on Fisher's exact test using the mITT population with baseline AFLS score of 2 on both cheeks or 3 on both cheeks.

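### The two secondary endpoints are each tested at two-sided 5% with no gate, order or alpha split, so the error rate over the pair is not controlled; the primary conclusion is unaffected.

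*SAP*

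**What the plan says.** The significance level is set once for all tests. SAP 5.1: "All statistical hypothesis tests will be performed at the 2-sided 5% significance level, unless stated otherwise". Protocol 10.3.1 agrees: "All statistical tests will be 2-sided hypothesis tests performed at the 5% level of significance for main effects".

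SAP 5.4.1 names two secondary endpoints, both at Month 1 of the control period: change in the converted FACE-Q score, and AFLS responder status. SAP 5.4.2 gives each its own between-group test. For FACE-Q it is "a 2-sided 2-sample t-test, if the normality assumption holds, otherwise, the Wilcoxon rank-sum test will be used". For AFLS, in the subset scoring 2 on both cheeks or 3 on both cheeks at baseline, the "95% CI for the risk difference and p-value will be estimated based on Fisher's exact test using the mITT population".

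The success rule in SAP Section 2 concerns ACSS only. It opens "If the 2-sided p-value is less than 0.05 and the responder rate is greater for" the product, and it then declares superiority. It does not mention the secondaries.

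Protocol 10.3.1.3 begins "The first secondary effectiveness variable is subject responses on the FACE-Q Satisfaction with Skin questionnaire" and then calls AFLS the other one. No testing sequence is attached to those words.

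No gate, order of testing, alpha split or multiplicity procedure appears in SAP Sections 2, 5.1, 5.3 or 5.4, or in protocol 10.3.1. All other effectiveness endpoints are descriptive (SAP 5.5) and no interim analysis is planned (SAP 5.8). The family at issue is therefore exactly these two tests.

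**The concern.** Protocol 3.1 states "This protocol is designed as a pivotal study to collect safety and effectiveness data" in support of FDA approval. In such a study, a secondary result reported as significant will be read as confirmatory unless the plan says otherwise. Under the plan as written, either secondary could be reported at p < 0.05 with no control over the pair, and nothing formally prevents this even if the primary is not met.

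Two features make the secondaries look more than descriptive. AFLS has its own power calculation at the full 5% level (SAP Section 3). Protocol 9.3.2 supports the choice of FACE-Q by noting that these questionnaires were developed with approval and labelling claims in view.

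At stake is how far a secondary claim can be trusted. A rule chosen after the results are known cannot give the same protection.

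**Working it through.** **Inputs**
- Two-sided 5% per test: SAP 5.1, protocol 10.3.1.
- Two secondary tests: SAP 5.4.1 and 5.4.2.
- Primary: 112 v 56, 80% v 40%, Fisher's exact test, stated power 99.9% (SAP Section 3).
- AFLS: 72 v 36, 80% v 45%, Fisher's exact test, stated power 94.4% (SAP Section 3).
- Correlation between the two test statistics: not in the documents, so a range is assumed.
- FACE-Q power: not in the documents, so 90% to 99% is assumed where needed.

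**1. The plan's own figures.** Exact enumeration of the two binomials with two-sided Fisher's test at 0.05 gives 94.40% for AFLS (stated 94.4%) and 99.91% for ACSS (stated 99.9%). Both reproduce.

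**2. Chance of at least one false rejection, both secondary nulls true, nominal level.** Under independence, 1 − 0.95² = 0.0975. For false claims of benefit only, 1 − 0.975² = 0.0494, against 0.025 for one test. With correlated statistics (bivariate normal, critical value 1.96):

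| Assumed correlation | Any false rejection | False claim of benefit |
|---|---|---|
| 0 | 9.75% | 4.9% |
| 0.3 | 9.5% | 4.8% |
| 0.5 | 9.1% | 4.5% |
| 0.7 | 8.3% | 4.2% |
| 0.9 | 7.0% | 3.5% |

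**3. Allowing for Fisher's conservatism.** At 72 v 36, the actual two-sided size of the AFLS test is 3.2% at a common responder rate of 10% and 3.9% at 45%; other rates up to 80% fall between. With FACE-Q at 5% and independence:
- lower: 1 − 0.95 × (1 − 0.0323) = 0.081
- upper: 1 − 0.95 × (1 − 0.0393) = 0.087

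For benefit only, the AFLS size is 1.24% to 2.16%:
- lower: 1 − 0.975 × (1 − 0.0124) = 0.037
- upper: 1 − 0.975 × (1 − 0.0216) = 0.046

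**4. What a gate on the primary alone would do.** If the product works on ACSS as assumed, the gate opens 99.9% of the time. The pair's error under independence is then 0.999 × 9.75% = 9.74%. The protection has to come from ordering or splitting the two secondaries.

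**5. Cost of control to AFLS power** (the primary gate itself costs at most about 0.1 point, 100% − 99.9%)
- Bonferroni, 2.5% each: exact power 91.0%.
- Holm: AFLS is rejected at 2.5%, or at 5% if FACE-Q is rejected at 2.5%. Power therefore lies between 91.0% and 94.4%. With FACE-Q power of 90% at the 2.5% level and independence, it is 0.910 + 0.90 × (0.944 − 0.910) = 94.1%.
- Fixed sequence with FACE-Q first, independence: 0.944 × 0.90 = 85.0% to 0.944 × 0.99 = 93.5%.
- Fixed sequence with AFLS first: AFLS stays at 94.4%, and FACE-Q bears the dependence. Its cost cannot be computed, because no effect size or SD is given.

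**The case against.** The strongest reply is that the documents attach no claim to either secondary. Study success rests on ACSS alone, the indication is cheek skin smoothness (protocol Appendix 6), and no superiority statement is written for FACE-Q or AFLS. Protocol 3.1 says the study supports approval, not that each secondary supports labelling. The remark on labelling claims in protocol 9.3.2 describes how the instruments were developed, not what the sponsor intends here. This stands. It is why declaring both endpoints supportive is an acceptable remedy, but the plan does not make that declaration either.

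A reader might infer that the chance of a false secondary claim in this study is nearly 10%. The documents do not support that reading. The 9.75% requires both nulls true, independence and nominal test size, and it counts rejections in favour of no treatment. If only one null is true, the chance of a false rejection is 5% with no adjustment at all. The superiority rule is directional, and protocol 10.3.1.3 analyses AFLS in the same way as ACSS, so the benefit-only column is the closer measure of a false claim. What survives is the ratio: 4.94 / 2.5 = 1.98 under independence and 4.17 / 2.5 = 1.67 at correlation 0.7.

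A reader might also infer that the protocol already holds a testing hierarchy, FACE-Q then AFLS, that the SAP neglects. It does not: first and other are only the order of listing. Adopting that order would make AFLS, the only secondary with stated power, depend on an endpoint with none.

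Finally, the two statistics might be highly correlated, which would shrink the problem. That is possible but not obvious. FACE-Q is rated by unblinded subjects, and AFLS by a blinded evaluator in about 65% of subjects.

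**Conclusion.** The gap is real and present in both documents: two formal secondary tests at full alpha, with no control over the pair. Its size is moderate. With both secondary nulls true, the nominal error is 9.75% under independence, falling to 8.3% at correlation 0.7, and about 8.1% to 8.7% under independence once the actual size of Fisher's test is used. In terms of false benefit, it is about 4.2% to 4.9% nominally against 2.5%. These figures rest on assumed correlations and, for Fisher's size, on common responder rates of 10% to 80%.

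The primary test is a single test at 5% and is not inflated by this. The possibility of a secondary claim after a failed primary carries little weight on the plan's own assumptions. How much the gap matters depends on whether the sponsor intends a secondary claim, which the documents do not say. This is a cheap improvement to the plan, not a threat to its main conclusion.

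**What to change.** Before database lock, the point by which protocol 10.3 requires the SAP to be final, add a paragraph to SAP 5.4.2. It should state that the secondaries are tested only if the primary is met, and that the pair is controlled at two-sided 5% by one of the following:

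- **Holm.** Neither endpoint depends wholly on the other. The cost is a loss of AFLS power of at most 3.4 points (94.4% − 91.0%).
- **Fixed sequence**, each test at 5%, in an order the sponsor chooses and states in advance. There is no alpha cost, but the second endpoint cannot be claimed if the first fails.

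The choice depends on which claim the sponsor values more. If no secondary claim is intended, state instead that both endpoints are supportive and that their p-values are nominal.

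Each option is a short SAP text change, with no extra patients and no change to the sample size.

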5.2. Participant Dispositions

The number of participants in each of the 6 study populations (mITT, Completers, Safety, VT, VRT, and Fitzpatrick safety cohort) will be summarized by treatment group.

The summary of study disposition will be provided for all screened participants overall or by study intervention group as randomized for the following:

- Number of participants screened (overall)
- Number of participants randomized; this number will be used as the denominator to compute the following percentages
- Number of participants treated as randomized
- Number of participants not treated as randomized

For mITT Population during CP

- Number of participants completed Control Period
- Number of participants discontinued during Control Period
- Reasons for discontinuation during Control Period

JUVÉDERM VOLITE™ XC

For VT Population after CP

- Number of participants who continued after Control Period
- Number of participants who completed the Follow-up Period
- Number of participants who discontinued during the Follow-up Period
- Reasons for discontinuation during the Follow-up Period

For VRT population during the RP

- Number of participants who received repeat treatment
- Number of participants who completed the RP
- Number of participants who discontinued during the RP
- Reasons for discontinuation during the RP

For mITT Population during the study

- Number of participants who completed the study
- Number of participants who discontinued from the study
- Reasons for discontinuation from the study

A participant is considered to have completed the study if he/she has completed all phases of the study including the last visit. Treatment group participants who elect not to receive repeat treatment are considered completers if they complete the Month 6 visit. Control group participants who elect not to receive treatment are considered completers if they complete the Month 1 visit.

5.3. Primary Effectiveness Endpoint Analysis

5.3.1. Definition of Endpoint

The primary effectiveness endpoint is the ACSS responder status at Month 1 in CP based on EI's assessment. A responder is defined as a participant who achieves at least 1-point improvement (reduction) from baseline on the ACSS scale (described in Table 5-2) on both cheeks.

Table 5-2 Allergan Cheek Smoothness Scale

Score	Grade	Description
0	None	Smooth visual skin texture
1	Minimal	Slightly coarse and uneven visual skin texture
2	Moderate	Moderately coarse and uneven visual skin texture; may have early elastosis
3	Severe	Severely coarse visual skin texture, crosshatched fine lines; may have some elastosis
4	Extreme	Extremely coarse visual skin texture, crosshatched deep creases; extreme elastosis

5.3.2. Main Analytical Approach

The missing data in ACSS at Month 1 of CP will be imputed using the Multiple Imputation (MI) method for the mITT population as follows:

Step 1: The missing data will be imputed by cheek side and treatment group using the Fully Conditional Specification (FCS) method with seed = 820403 and nimpute = 30 based on the following model:

$$\text{Month 1 ACSS} = \beta_0 + \beta_1 \times \text{Age} + \beta_2 \times \text{Baseline ACSS}$$

Step 2: After imputation, the changes from baseline will be calculated, from which the responder status in ACSS at Month 1 of CP will be determined.

Step 3: Each complete dataset obtained from Steps 1 and 2 will be analyzed using SAS procedure FREQ

Step 4: The pooled results will be obtained using PROC MIANALYZE

The number and proportion of participants who achieved at least 1-point improvement from baseline at Month 1 of CP will be tabulated by treatment group. The aggregated responder rates by treatment group and the associated p-value and 95% CI estimated based on the normal approximation to assess the difference in the ACSS responder rate at Month 1 of CP between JUVÉDERM VOLITE XC and the no-treatment control will be presented. If the 2-sided p-value is less than 0.05, then the ACSS responder rate at Month 1 in JUVÉDERM VOLITE XC is statistically significantly different from that in the no-treatment control group during the control period. Furthermore, if the responder rate is greater for JUVÉDERM VOLITE XC than the no-treatment control group, then VOLITE will be considered superior to the no-treatment control group.

The detailed SAS codes are as follows:

```
proc mi data=adeff seed=820403 nimpute=30 out=mi;
  by trt01p cheek;
  class acss0 acss1;
  fcs logistic(/details);
  var age acss0 acss1;
run;
data lmi rmi; *separate imputed datasets by cheek side;
  set mi;
  if cheek='Left' then output lmi;
  if cheek='Right' then output rmi;
run;
data all; *obtain responder status variable;
  merge lmi rmi;
```

JUVÉDERM VOLITE™ XC

```
by _imputation_ subjid;
ldiff=lacss0-lacss1;
rdiff=racss0-racss1;
resp=0;
if ldiff >= 1 and rdiff>=1 then resp=1;
run;
ods output RiskDiffCol2=risk(where=(index(row,'Total')=0));
proc freq data=all;
  by _imputation_;
  tables trt01p*resp/riskdiff;
run;
proc sort data=risk; by row;
ods output VarianceInfo=Variance1;
ods output ParameterEstimates=Param1;
proc mianalyze data=risk;
  by row;
  modeleffects risk;
  stderr ase;
run;
```

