Procedure	Randomization ^a	Month 1 Study Exit visit
Visit Window (Days)		-2/+7
Urine pregnancy test ^b	X	
Inclusion/Exclusion criteria (TI, EI, Subject)	X	
FACE-Q Satisfaction with Skin questionnaire (Subject)	X	X
FACE-Q Appraisal of Lines-Overall questionnaire (Subject)	X	X
ACSS (EI)	X	X
AFLS (EI)	X	X
Skin hydration (EI)	X	X
2D facial imaging	X	X
Randomization	X	
Weight measurement		X
Concomitant medications, procedures, treatments	Continuous Monitoring	
Adverse events	Continuous Monitoring	

^a Randomization must occur within 30 days of screening; screening visit and randomization visit can occur on the same day if subjects do not require washout. If screening and randomization visits occur on the same day, inclusion/exclusion criteria and urine pregnancy testing need not be repeated.

^b For female subjects of childbearing potential; administered and confirmed negative prior to randomization. A female subject is not considered of childbearing potential if she has been postmenopausal for at least 1 year or does not have a uterus at the time of study entry.

Table 2-4 Control Group Procedures (Delayed Treatment Period)

Procedure	Initial Tx ^a	Day 3 after Initial Tx	Touch-up Tx Day 30 ^b	Day 3 after Touch-up Tx	Month 1	Month 2	Month 4	Month 6 Study Exit Visit
Visit Window (Days)	+7	+2	-2/+7	± 2	-2/+7	±7	±7	±7
Urine pregnancy test ^c	X		X					X
Snellen visual acuity (TI or designee)	X ^d	X	X ^d	X	X			
Confrontational visual fields (TI or designee)	X ^d	X	X ^d	X	X			
Ocular motility (TI or designee)	X ^d	X	X ^d	X	X			
Treatment procedure ^e	X		X					
Procedural pain	X							
Safety e-diary ^f (Subject)	X		X					
FACE-Q Recovery Early Life Impact questionnaire (Subject)		X						
2D facial imaging		X	X		X	X	X	X
FACE-Q Satisfaction with Skin questionnaire (Subject)			X		X	X	X	X
FACE-Q Appraisal of Lines-Overall questionnaire (Subject)			X		X	X	X	X
Natural look and feel assessment (Subject)			X		X	X	X	X
GAIS (Subject)			X		X	X	X	X
ACSS (EI)			X		X	X	X	X
AFLS (EI)			X		X	X	X	X
Skin hydration (EI)			X		X	X	X	X
Weight measurement								X
Concomitant medications, procedures, treatments					Continuous Monitoring			
Adverse events					Continuous Monitoring			

^a Initial treatment for the control group is offered only after completion of 1 month of no-treatment control period.

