6.2. Appendix 2: Changes to SAP Version 1 Analyses

The following are changes to [version 1](#) of SAP:

1. The naming of the analysis population for the sensitivity analysis of primary endpoint, ACSS responder status at Month 1 was changed from “Completer Population” to “Observed Primary Endpoint” in Section 4. The definition of this population refers to the completion of the primary timepoint visit (ie., Month 1 of CP). This naming change is aimed to avoid potential confusion with study completion.
2. The wordings of “overall converted score” were specified for the analyses of FACE-Q Satisfaction with Skin, FACE-Q Appraisal of Lines, and FACE-Q Recovery Early Life Impact in Sections 4, 5.4, 5.5 and 5.6.5 to enhance clarity and consistency with Appendix 6.5.
3. The cut-off for the of FACE-Q Satisfaction with Skin as one of the definitions for Fitzpatrick Safety Cohort was changed from 39 for the overall raw score to 69 for the overall converted score in Table 4-1.
4. The definition of “baseline” for the effectiveness and safety variables in Section 5.1 was changed to “the last non-missing assessment prior to the latter of randomization or first treatment in the control period” due to possibility of participants who were mis-treated (ie., either randomized to Volite but was not treated or randomized to Control but received Volite)
5. The multiple imputation for the primary effectiveness analysis described in Section 5.3.2 was revised to (1) include the baseline ACSS score and age in the model based on the correlation with the primary endpoint to be imputed (ie., ACSS score at Month 1 of CP) and (2) number of imputed dataset is increased from 5 to 30 to reduce variability and increase the efficiency of estimates
6. The derivation for skin hydration and analyses of following variables were added to other effectiveness analyses in Section 5.5:
 - a. raw value and change from baseline in ACSS
 - b. raw value and change from baseline in AFLS
 - c. item scores and aggregated categories for FACE-Q Satisfaction with Skin
 - d. item scores and aggregated categories for FACE-Q Appraisal of Lines
7. The analysis of ISR in Section 5.6.3 was revised to include: (1) ISR by maximum severity for summaries up to 30 days and beyond 30 days after treatment, (2) analysis of “other symptoms” based on the coded terms assigned by the Medical Safety Physician

JUVÉDERM VOLITE™ XC

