6.4. Data Handling Convention

6.4.1. Analysis Window

6.4.1.1. Effectiveness

Table 6-2, [Table 6-3](#), and [Table 6-4](#) below present the timepoints assigned for analyses and the corresponding range of study days for all the scheduled and unscheduled visits with complete dates. If a scheduled visit with incomplete date is available with no other visits with complete date during the visit window, then the visit with incomplete date may be used for analysis and the nominal visit will be used as the visit window (eg, if the only assessment collected for Month 2 visit window is on a Month 2 eCRF with incomplete date, then those data will be used for the Month 2 assessments).

If multiple assessments were taken within an analysis window, the assessment obtained on the day closest to the target day will be used; in the case of a tie, the assessment obtained on the later day will be used in the analysis.

Analysis visit windows for effectiveness endpoints are defined as follows:

If analysis date \geq reference date, then

$$\text{Analysis day} = \text{analysis date} - \text{reference date} + 1$$

If analysis date $<$ reference date, then

$$\text{Analysis day} = \text{analysis date} - \text{reference date}$$

Table 6-2 **Effectiveness Analysis Visit Definitions for Treatment Group and Control Group during Treated Period**

Scheduled Visit for Effectiveness Measure	Target Day of the Visit	Analysis Visit Window
Screening ^a	N/A	Screening visit; no more than 30 days prior to randomization
Baseline	N/A	Randomization/Initial Treatment visit
Last Treatment ^b	Day 1 of Last Treatment	Day 1
Month 1	Day 31 Post Last Treatment	Day 2 to Day 46
Month 2	Day 61 Post Last Treatment	Day 47 to Day 91
Month 4	Day 121 Post Last Treatment	Day 92 to Day 151
Month 6	Day 181 Post Last Treatment	Day 152 to Repeat Treatment Date (if applicable) or Study Exit Date, whichever is earlier

^a Participants may have screening and randomization on the same day. In such cases, only randomization visit is relevant

^b The last treatment refers to the latter of initial treatment or touch-up treatment (if applicable)

Table 6-3 Effectiveness Analysis Visit Definitions for Control Group during Control Period

Scheduled Visit	Target Day of the Visit	Analysis Visit Window
Randomization Day	Day 1	N/A
Month 1	Day 31	Day 2 to Optional Treatment Date or Study Exit Date, whichever is earlier.

Table 6-4 Effectiveness Analysis Visit Definitions for Treatment Group during Repeat Treatment Period

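### The primary multiple imputation draws each cheek separately although response needs both, which lowers the imputed responder rates if the cheeks agree; the printed SAS code also cannot produce the primary result.

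*SAP*

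**What the plan says.** SAP 5.3.1 defines a responder as a "participant who achieves at least 1-point improvement (reduction) from baseline on the ACSS scale (described in Table 5-2) on both cheeks".

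Step 1 of SAP 5.3.2 says: "The missing data will be imputed by cheek side and treatment group using the Fully Conditional Specification (FCS) method". The printed PROC MI call matches this. It runs "by trt01p cheek", and its variables are age, that cheek's baseline and that cheek's Month 1 score. Responder status is derived only afterwards, in Step 2, with statements such as "ldiff=lacss0-lacss1".

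Item 5 of SAP Appendix 2 explains the current model. Version 2 was revised to "include the baseline ACSS score and age in the model based on the correlation with the primary endpoint to be imputed". The opposite cheek's Month 1 score was not considered.

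SAP 5.3.3 adds a tipping-point analysis and an observed-case analysis, neither of which uses imputation by cheek.

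**The concern.** The imputation does not match the endpoint. Response is a joint event on two cheeks of one face, rated at one visit and, as Protocol Section 9 recommends, by the same evaluator throughout. Separate models turn its probability for a missing participant into a product of two cheek probabilities. Under positive residual agreement that product is too small. If only one cheek is missing, the observed cheek is ignored.

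The primary estimate, confidence interval and p-value all pass through this step. The shortfall is larger in the control arm than in the VOLITE arm at the planning rates, so it does not cancel in the difference.

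The code is a second, separate problem. It is presented as the detailed implementation but cannot deliver the primary result as printed.

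**Working it through.** **Inputs from the documents.** Both-cheek responder rates of 80% (VOLITE) and 40% (control), 112/56 evaluable, 210 randomized 2:1 and 20% attrition over the study (SAP Section 3); 30 imputations (SAP 5.3.2).

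**Assumed, because the documents do not give it.** The residual left/right correlation, on a latent normal scale, is varied over 0.5, 0.7 and 0.9. Month 1 missingness by arm is varied from 5% to 20%.

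**1. The plan's own figures.** Exact two-sided Fisher power for 112 vs 56 at 80% vs 40% is 99.91% (stated: 99.9%). 168 / 0.80 = 210 (stated: 210). Both reproduce.

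**2. Bias per missing participant.** Let P be the true both-cheek rate and p the single-cheek rate. Solve P = Φ₂(z, z; ρ) with z = Φ⁻¹(p). Separate imputation gives p², so the bias is b = p² − P.

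| ρ | VOLITE p | p² | b (points) | Control p | p² | b (points) |
|---|---|---|---|---|---|---|
| 0.5 | 0.879 | 0.772 | -2.8 | 0.564 | 0.318 | -8.2 |
| 0.7 | 0.866 | 0.750 | -5.0 | 0.526 | 0.277 | -12.3 |
| 0.9 | 0.843 | 0.710 | -9.0 | 0.472 | 0.222 | -17.8 |

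At ρ = 0.9 the two cheeks agree on response in 1 − 2(p − P) = 91% (VOLITE) and 86% (control) of participants. If baseline 2 vs 3 shifts the both-cheek rate by 10 points either side of the arm mean and is in the model, the biases at residual correlation 0.9 are -8.6/-17.0, so baseline removes little. For a control participant with one cheek missing and the other seen to improve, the true response probability is 0.40/0.472 = 85%, but the model imputes 47%.

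A second model, P = p² + ρp(1 − p), gives the same picture. At ρ = 0.7 the imputed rates are 70.6% and 22.5% instead of 80% and 40%.

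**3. Bias in the difference.** This is m_V·b_V − m_C·b_C, where m is the missing fraction. At ρ = 0.9:

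| Missing VOLITE/control | Bias (points) |
|---|---|
| 5%/5% | +0.4 |
| 10%/10% | +0.9 |
| 20%/20% | +1.8 |
| 5%/20% | +3.1 |
| 10%/5% | about 0 |
| 20%/5% | -0.9 |

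For example, at 5%/20%: 0.05 × (-9.0) − 0.20 × (-17.8) = +3.1. The planning rate is only a ceiling ("the control group is assumed to have at most a 40% responder rate"). With 20% missing in both arms, a control rate of 20% gives +0.9 and one of 10% gives -0.2.

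**4. Error rates.** Simulation used 140/70 participants, data missing completely at random within arm, 30 imputations, Rubin pooling, a Wald difference and 20,000 trials per scenario (Monte Carlo SE at most 0.2 points). Upper-tail error with both true rates at 40%:

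| Missing VOLITE/control | ρ | By cheek | Joint |
|---|---|---|---|
| 5%/20% | 0.5 | 4.1% | 2.9% |
| 5%/20% | 0.7 | 5.0% | 2.9% |
| 5%/20% | 0.9 | 6.6% | 3.0% |
| 5%/10% | 0.9 | 3.9% | 2.8% |
| 5%/5% | 0.5 to 0.9 | 2.8–3.0% | 2.8–2.9% |
| 10%/5% | 0.5 to 0.9 | 2.3–2.5% | 2.9% |
| 20%/5% | 0.9 | 1.3% | 2.9% |

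With no missing data the normal-approximation test already has about 3% upper-tail error, so only the excess over that is due to the by-cheek step. At 80% vs 40% and ρ = 0.9, interval coverage is 93.0% against 94.6% with joint imputation when 20% are missing in both arms, and 94.2% against 94.5% when 5% are.

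**5. The code.** PROC MI carries `acss0` and `acss1`. The later DATA step reads `lacss0`, `lacss1`, `racss0` and `racss1`, which no printed step creates. PROC MI output is ordered by arm and cheek, but the merge is by `_imputation_` and `subjid` with no sort. Even after a sort, both differences are missing and `resp` stays 0 for everyone. Over all 50 patterns (baseline 2 or 3; left and right Month 1 scores 0 to 4) the printed step flags 0 responders. With the variables named correctly it flags 2 × 2 + 3 × 3 = 13. With a single response column there is no column-2 risk to pool.

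**The case against.** The mechanism is hard to dispute; the weight is open to argument.

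- **The worst case needs more controls missing.** The plan gives controls a reason to attend: "Initial treatment for the control group is offered only after completion of 1 month of no-treatment control period" (Protocol Table 2-4). Their Month 1 window is also generous: "Day 2 to Optional Treatment Date or Study Exit Date, whichever is earlier" (SAP Table 6-3). The VOLITE window closes at Day 46 after last treatment. Both features point to fewer missing controls, where the error is conservative. This stands, but the plan does not fix the pattern.
- **20% is whole-study attrition.** It is an upper case for Month 1. At 5% missing in both arms the bias in the difference is +0.3 to +0.4 points and the error rate is not inflated. This stands.
- **The correlation is assumed.** This also stands: confidence attaches to the mechanism, not the size.
- **The sensitivity analyses show whether the conclusion is fragile.** The tipping-point grid covers every possible count of imputed responders. That protects the conclusion, but does not correct the primary estimate or interval.
- **The protocol's own rule can be worse.** Protocol 10.3.1.2 counts missing as non-response. At 5%/20% missing that gives 0.95 × 80 − 0.80 × 40 = 44, a bias of +4.0, and +6.0 when both rates are 40%. The by-cheek step gives +3.1 and about +2.6. This is useful context, but does not justify a mis-specified imputation.
- **The code fault is editorial.** Steps 1 to 4 are clear and the fault would show when run. Largely true. The exception is an input file that already holds unimputed columns under those names: once sorted, the code would then count missing participants as non-responders without warning.

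**Conclusion.** The concern holds and should be fixed. Under any positive agreement beyond age and baseline, imputation by cheek understates the both-cheek rate for missing participants in each arm. The direction in the treatment difference is not fixed: at ρ = 0.9 and 80%/40% it ranges from -0.9 to +3.1 points over the missingness patterns examined. The 6.6% upper-tail error is an extreme case, since it needs strong correlation and four times as much missingness among controls. With few missing at Month 1 the effect is small, and the reverse pattern is conservative. A true 40-point effect would not be overturned. The sizes rest on an assumed correlation, on assumed Month 1 missingness and, in the simulation, on data missing completely at random within arm. The code defect does not depend on any of these.

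**What to change.** Restructure to one row per participant and impute by treatment group only. Put left and right Month 1 ACSS, age and baseline ACSS in one FCS model, so that each cheek's draw conditions on the other. Keep both baselines on the row for the change scores. Outside the Fitzpatrick V/VI safety cohort, which mITT excludes, Protocol 6.1 requires equal baseline scores, so one baseline term in the model normally suffices. Add the second if an mITT participant has unequal scores.

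If control-arm cells are too sparse, impute both-cheek responder status directly with a logistic model on age and baseline, first setting anyone with an observed non-improved cheek to non-response. This fallback ignores an observed improved cheek, so the joint model is preferable.

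Derive `resp` from that row, define the left and right variables explicitly, add any sort that is needed, and test the code on dummy data. The change applies whether multiple imputation stays primary or becomes a sensitivity analysis. It costs a few lines of SAP text and code before database lock and needs no new data.
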